Implementation of 'NAVIGATE' in Ontario aims to help youth and emerging adults (YEA) suffering from a first episode of psychosis (FEP). Although Ontario already has early psychosis intervention (EPI) programs, our team's recent work has identified major challenges of delivering coordinated care, particularly those elements of care that enhance recovery. These challenges also exist nationally and internationally. By building on the already existing EPI community of practice through the Early Psychosis Intervention Ontario Network, we will implement NAVIGATE with the help of CAMH's Provincial System Support Program facilitators. The use of tele-videoconferencing through ECHO Mental Health Ontario, and the processes and protocols that ECHO provide us with an opportunity to ensure sustainability. Using health administrative data held at the Institute for Clinical Evaluative Sciences (ICES), we can examine system-level outcomes, including hospitalizations, emergency department visits, and outpatient physician visits of YEA suffering from a FEP who are treated with NAVIGATE compared with those treated in EPI programs without NAVIGATE and those who are not treated in EPI programs. In addition, we can also evaluate health care costs. Prior to initiating this project, we obtained the input of YEA with an FEP and family members. We will also continue to measure engagement across the study. This work fulfills the innovative clinical trial mandate through its implementation and measurement plan, along with the strategy for patient-oriented research through the involvement of patients, family members, and policy makers as equal partners.

2. Introduction and Background/Rationale

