ii). Institute for Clinical and Evaluative Sciences (ICES) Data: A Unique Opportunity to Evaluate System-Level Impact – Meeting the Mandate of the Innovative Clinical Trial (ICT): Using data from ICES, which captures all physician and hospital-provided insured services in Ontario, we will compare population-based outcomes (hospitalizations, emergency department visits, suicide attempts and mortality) with two comparison groups: 1) all EPI program FEP patients who have not been part of the NAVIGATE trial; and 2) all FEP patients who are not attached to EPI programs. All EPI programs in Ontario report their service utilization data through the Ontario Common Assessment of Need (OCAN) dataset (OCAN is linked to ICES data). While accuracy of data within OCAN is variable, we have confirmed that we can accurately ascertain the initiation date of all EPI patients by sex within Ontario through ICES linkage. The ability to link NAVIGATE's primary clinical and implementation data with ICES data, and the capacity to identify all FEP patients in Ontario (whether treated in EPI programs or not) allows for a meaningful, valid, and highly generalizable comparison of outcomes. The use of propensity score methods will address confounding associated with observational studies, and mimics some of the characteristics of a randomized controlled trial⁵¹. Since outcome data across all comparison groups are routinely collected by ICES, this dramatically reduces the time and cost of a randomized controlled trial (RCT) (thus fulfilling the ICT mandate), because the study does not require costly, extensive follow-up.

ICES has developed a costing macro that we have used to study health care costs among individuals in Ontario with schizophrenia⁵². The costing macro ensures that we have the capacity to determine costs associated with NAVIGATE relative to EPI usual care and no EPI care, a key implementation outcome. Cost estimation adds to the feasibility and policy-relevance of scaling up.

3. Statement of Objectives and Hypotheses

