3.1. Primary Objectives

1. Assess whether implementation of NAVIGATE leads to improvement in fidelity to the EPI standard (using the FEPS-FS).
2. Compare system-level outcomes, i.e. days in hospital, emergency department visits, suicide attempts, mortality, and system costs among patients receiving NAVIGATE compared with patients at other EPI sites not receiving NAVIGATE and patients with psychotic disorders who are not enrolled in EPI.
3. Determine longitudinal change in functioning and symptoms in NAVIGATE patients.
4. Evaluate patient and family member engagement according to the SPOR framework.

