Staff interview (value and feasibility)*	CFIR adapted					•
Implementation outcomes (staff capacity)						
Staff survey (knowledge and skills)	ECHO survey	•			•	•

* includes perceptions of ECHO support

System Level Outcomes + Analytic Plan (Objective 2):

Data Sources: The primary data collected for patients of the NAVIGATE protocol will be linked deterministically to data sources held at the Institute for Clinical Evaluative Sciences (ICES) via their unique health card number. The patient-level outcomes are enhanced by routine system-level outcome measurement and the capacity to compare outcomes among NAVIGATE subjects with two control populations: 1) FEP subjects in Ontario who are not part of the NAVIGATE trial but are receiving EPI services; and 2) FEP patients with no EPI contact. Only NAVIGATE patients who have consented will have their program-level data linked to ICES. The following ICES data sources will be used: the Ontario Health Insurance Plan (OHIP) which covers data for physician billings; the Canadian Institute for Health Information Discharge Abstract Database (CIHI-DAD) which covers all hospitalizations; the Ontario Mental Health Reporting System (OMHRS), covering adult mental health hospitalizations; the National Ambulatory Care Reporting System (NACRS) for emergency department (ED) visits; the Ontario Drug Benefits (ODB) which provides information on all prescriptions covered by the ODB (based on financial need for those under 65 years of age and universally for young people up to age 25); and the Registered Persons Database (RPDB) containing information on patient demographics and deaths. The Ontario Community Assessment of Need (OCAN) database captures all first episode patients attached to EPI programs in Ontario. OCAN will be used to develop a control population of FEP patients who are attached to non-NAVIGATE EPI programs. Statistics Canada estimates will be used to derive neighbourhood income and rurality. These data sources can be linked via the encrypted health card number such that all the information is available for each individual, and de-identified.

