Matched Controls: Each NAVIGATE subject will be matched to two types of subjects: 1) FEP patients attached to EPI programs who are not participating in the NAVIGATE trial; and 2) FEP patients with no EPI program attachment. Control cases will be matched to NAVIGATE subjects based on OCAN admission date for patients attached to EPI programs and at time of first diagnosis for those patients not attached to EPI programs. Patients with no EPI attachment will be identified using a validated algorithm that identifies all incident cases of psychotic disorders⁶⁹. The diagnostic codes vary by database and included ICD-9, ICD-10, DSM-IV codes. In order to be a FEP case among the non-EPI attached control group, subjects will not have had a non-affective psychotic disorder diagnosis within five years of the matching date. We will use propensity score matching to create the 2 comparison groups of non-NAVIGATE subjects. Propensity score matching mimics the characteristics of a randomized trial using observational data. A propensity score defined as the probability that a person is in the “exposed” category. In this case, the exposure condition is access to the NAVIGATE protocol. The propensity score is developed using logistic regression to model exposure to NAVIGATE as a function of observed covariates to yield a probability of NAVIGATE access for each subject. The propensity score model will include sociodemographic characteristics, clinical factors, and prior service use (defined below). We will match non-NAVIGATE to NAVIGATE subjects based on year of index diagnosis and caliper of the propensity score. Non-NAVIGATE Subjects will be assigned the same admission date as NAVIGATE subjects.

System Outcomes (Hospitalization, ED visits, suicide attempts): Our primary outcome is number of psychiatric hospitalization days in the year following NAVIGATE admission. We will include secondary outcomes, such as ED visits and suicide attempts. Hospitalization-based outcomes will include number of psychiatric hospitalizations and time to first psychiatric hospitalization. We will measure psychiatric emergency department visits with a year of admission as well as ED visits for suicide attempts. Visits to psychiatrists and primary care physicians will also be counted^{70,71}. Visits to primary care physicians will be stratified as mental health related versus non-mental health related based on a previously validated algorithm⁷².

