All patients will be given the option to participate. Participation in the study is voluntary. The decision to participate will not affect patients' receipt of treatment or clinical services including NAVIGATE. Participants will be informed that they have the option of terminating their participation at any time, without consequence and that no new data will be collected on them. Any existing data will be de-identified.

Participants will be provided with a clear explanation of the objectives, procedures, risks and benefits of the study and all questions will be answered. Questions will be asked of participants to ensure that they understand the nature of the research, the risks and potential benefits of study participation, and their rights as research participants prior to obtaining their signature on the informed consent document. Because we believe that consent is an ongoing process in any study, we will continue to educate participants about the nature of the research and address any questions that may arise throughout the course of the study. We are not planning to use proxy consent.

The delegated research staff will obtain collateral information (if necessary) from the sites' clinical team to confirm diagnosis or obtain other clinically relevant information in the research study.

b) Patient's family member participation

As a part of the informed consent process with patients, the research team will ask the patient if we can reach out to one of their family members in order to tell them about the study. The research team will also briefly explain that the family member participation involves the completion of brief surveys about their (the patient's) functioning. If the patient consents, we will ask them to provide the contact information of a family member or caregiver. The research team will then contact the family member, introduce themselves, and read a brief consent script and ask them to provide an email address and/or cell phone number for the purpose of receiving a full consent form electronically. The research team will document this phone call in the study records, including whether email addresses/cell phone numbers were provided for research purposes. The electronic (web- or SMS-based, depending on what they provided) consent form will be sent immediately. If the participant (family member) clicks indicating that they do not consent, they will not be

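### The EPI control group has two conflicting definitions, and the matching rule as written admits patients who have access to NAVIGATE

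*Combined protocol and SAP*

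**What the plan says.** The EPI control group is described six times, in two ways.

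By non-participation in the trial:
- Section 2.1, item on ICES data: "all EPI program FEP patients who have not been part of the NAVIGATE trial".
- Section 4, System Level Outcomes, Data Sources, list of control populations: "FEP subjects in Ontario who are not part of the NAVIGATE trial but are receiving EPI services".
- Section 4, Matched Controls, the matching rule: "FEP patients attached to EPI programs who are not participating in the NAVIGATE trial".

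By program or site:
- Opening summary, before Section 2: "those treated in EPI programs without NAVIGATE".
- Section 3.1, Primary Objective 2: "patients at other EPI sites not receiving NAVIGATE".
- Section 4, Data Sources, sentence on OCAN: "OCAN will be used to develop a control population of FEP patients who are attached to non-NAVIGATE EPI programs".

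The Data Sources paragraph therefore holds both definitions. The Matched Controls paragraph also fixes what the propensity score models: "the exposure condition is access to the NAVIGATE protocol". On study refusal, Section 10(a) states that declining has no bearing on a patient's "receipt of treatment or clinical services including NAVIGATE". Section 2.1, where it explains how NAVIGATE answers Challenge 1, says that its elements are offered to every patient.

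**The concern.** Trial participation and NAVIGATE access are different things in this study. NAVIGATE is put in place for a whole program, while participation depends on individual consent to research assessments. A patient who declines at a NAVIGATE program is outside the trial but still within reach of the intervention. A control rule based on non-participation lets such a patient stand as an untreated comparator, against the exposure definition in the same paragraph.

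Only the NAVIGATE versus EPI comparison is at stake. It carries the primary system outcome (psychiatric hospital days in the year after admission) and the cost analysis. The comparison with patients who have no EPI attachment is unaffected. Two analysts could build different EPI control pools from this plan, and each could cite the text in support.

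**Working it through.** **1. Who is treated differently by the two definitions.** Non-participants at non-NAVIGATE programs are controls under both. Participants are controls under neither. The definitions part only on non-participants at programs that implement NAVIGATE: controls by the matching rule, not controls by Primary Objective 2 and the OCAN sentence.

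**2. Are these patients exposed?** Exposure is access to NAVIGATE (Section 4, Matched Controls). Declining the study leaves access intact (Section 10(a)), and the elements are offered to every patient (Section 2.1). So they are exposed by the plan's own definition. Access is not the same as receipt, which may be partial.

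**3. Does another step remove them?** OCAN is said to capture all first-episode patients attached to EPI programs in Ontario, so decliners are in it. Only consenting NAVIGATE patients have program-level study data linked at ICES (Data Sources), so study data would not flag a decliner. The label non-NAVIGATE, used in Matched Controls and in Statistical Analysis, is not defined. No explicit exclusion of participating programs' patients is stated.

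**4. How many such patients there may be.** Inputs from Section 3.3, Recruitment: 411 new patients a year across sites (2016); 400+ new patients and 300 recruits in months 12-24; about 25% who decline or are lost before the first visit.
- The plan's own arithmetic reproduces: 400 × (1 − 0.25) = 300.
- Non-participants from the stated floor: 400 − 300 = 100.
- At the 2016 intake: 411 − 300 = 111, and 111 / 411 = 27.0%.

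Months 6-12 would add 200 − 100 = 100, but some sites are not yet ready in that period, so this figure is left out. The 100 to 111 includes patients lost before their first visit. Late entry, allowed up to about a year into EPI care, also means that recruits need not come from the same intake window. It is an approximate count of non-participants.

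**5. What this does to the contrast.** Let Δ be the NAVIGATE effect on the mean, c the share of matched EPI controls who are non-participants at NAVIGATE programs, and r the fraction of Δ they receive. Assume that they otherwise resemble the other controls. The control mean moves by c × r × Δ, so the observed contrast is Δ × (1 − c × r). Neither c nor r is given: the size of the EPI pool and the matching ratio are not stated, and receipt among decliners is unknown. As assumed values only, c = 10% with r = 1 leaves 90% of the contrast, and c = 25% with r = 1 leaves 75%. With r = 0 there is no dilution at any c.

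**The case against.** The strongest reply is that the plan, read as a whole, already restricts the pool. The OCAN sentence says how the EPI control population is to be built and uses the program-level definition. Primary Objective 2 does the same. Matched Controls draws EPI controls by OCAN admission date and calls them non-NAVIGATE subjects, Statistical Analysis repeats that label, and modelling access as the exposure points the same way. On this view, harm needs an analyst to overlook several sentences.

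Much of this stands: program level is the more plausible intention. But Matched Controls is the operative text for building the groups, and its numbered rule is trial-level. The undefined label most naturally refers back to that rule. The list in Data Sources uses the broader wording in the same paragraph as the OCAN sentence, so neither clearly governs. If program level was always meant, the correction only records it.

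A second reply is that the weight of the problem is unknown. That is correct and limits the conclusion. The penetration analysis in Section 4 will not settle it. Although penetration is described in terms of all eligible program patients, the unit of analysis is the 400 patients, which matches the recruitment target. Receipt among decliners would not be measured.

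**Conclusion.** The contradiction is firm and rests only on the text. The matching rule, followed literally, admits controls who are exposed under the definition in its own paragraph. The consequence is conditional: dilution of the NAVIGATE versus EPI contrast in proportion to c × r, with neither quantity available. It should be settled before the cohort is drawn, but it does not show that a result would be wrong by any stated amount.

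Three stronger readings are tempting and not supported.
- A reader might infer a known bias toward no difference. Dilution pulls that way if decliners otherwise resemble the other controls, but they may differ in prognosis in either direction, so the net direction is open.
- A reader might take 100 to 111 as the number of contaminated controls. It counts non-participants approximately. How many would be matched, and how many would receive NAVIGATE, is not given.
- A reader might extend the point to patients admitted shortly before a site started NAVIGATE. The late-entry rule in Section 3.3 governs when patients may join the study. It does not say that those already in care are moved onto NAVIGATE.

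**What to change.** Use the program-level definition of Primary Objective 2 and the OCAN sentence in the three places that lack it: the ICES item in Section 2.1, the control list in Data Sources, and the matching rule in Matched Controls. In substance, EPI controls are first-episode patients attached to EPI programs that are not implementing NAVIGATE, and all patients of participating programs are excluded from this group whatever their consent status. Excluding those programs outright means that no rule about site start dates or overlapping follow-up is needed.

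First confirm that OCAN identifies the program. All EPI programs report to it, but Section 2.1 calls its accuracy variable and confirms only the initiation date by sex.

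The cost is wording in three places, one filter on program, and a somewhat smaller EPI control pool. The loss includes the roughly 100 to 111 non-participants of months 12-24 and those from other periods. The size of the remaining pool is not stated.

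The change does not address selection of consenting patients into the NAVIGATE arm. That is a separate matter and exists under either definition.

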iv) AFFORDABILITY System Outcome – Cost (i.e. Implementation Evaluation Outcome iv):

We will employ a costing algorithm developed in SAS®, and available at ICES⁷³, to estimate all direct patient-level health care costs incurred by the public third-party payer (Ontario Ministry of Health and Long-Term Care) across the three comparison groups. We will include costs of hospitalizations (both non-psychiatric and psychiatric); ED visits; physician services (i.e. primary care, psychiatry and other care) and diagnostics tests; outpatient prescription drugs for individuals covered under the provincial public drug insurance plan only (for individuals under 65 who receive social assistance and currently universally for individuals under age 25); home care; long-term care; and other care (this includes other ambulatory care, such as same-day surgery/procedures, cancer and dialysis clinic visits, and other hospital-based care, such as rehabilitation and complex continuing care). The costing methodology used in the algorithm will include a bottom-up/micro-costing approach to cost services at the individual level. This approach will make use of individual episodes of care or utilization in the health care system and attached prices (or costs or amounts paid) to each one. A top-down approach, which allocates corporate aggregate (i.e. institutional) costs to individual visits or cases/episodes of care, will be applied in cases where individual unit costs are not available (e.g. for institutional care settings). Assuming that all subjects will incur health care costs, we will use a generalized linear model with a gamma distribution and log link to model health care costs. Actual model parameters will be determined by the nature of the cost distributions.

Covariates: We will extract information on sociodemographic characteristics, including age, sex, neighborhood-level income quintile, and rurality of residence. Clinical covariates will include type of diagnosis (schizophrenia, schizoaffective disorder, etc.), source of index diagnosis (hospitalization, outpatient visit), and history of visits with alcohol- or substance-related diagnoses. We will also measure prior service use for mental disorders, including the number of prior visits for mental health reasons with the primary care physician, visits to psychiatrist, emergency department visits related to mental health and addiction conditions, and previous psychiatric hospitalizations.

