Statistical Analysis: Our primary outcome is days in hospital in the year following NAVIGATE admission. We will compare the three groups (NAVIGATE, non-NAVIGATE EPI, and non-EPI FEP patients) across all covariates listed above. We will subsequently model total hospital days adjusting for covariates. The regression model will be determined by the distribution of the dependent variables. If normally distributed, linear regression; if the distribution assumes a Poisson distribution, we will use Poisson regression. Secondary outcomes will be modeled using logistic regression (for binary outcomes) or Cox Proportional Hazard modelling (for time-to-event outcomes).

Patient-Level Outcomes – Analytic/Statistical Plan (Objective 3):

Since this is an implementation study, based on the already established effectiveness of NAVIGATE, we do not have a comparator arm. We will compare patient level outcome data from our study with the aggregate data from the original NAVIGATE study to assess comparability of the intervention in different jurisdictions, using a matching-adjusted indirect comparison (MAIC) model. In this approach we adjust the population receiving the intervention to match the average baseline characteristics with a reference population. We then compare outcomes across balanced populations. This is facilitated by the use of identical patient-level outcome measures as in the RAISE study, and the collection of similar baseline characteristics that might influence outcome (e.g. age, education, sex, race, baseline illness severity). With a large number of patients, we will also explore sex-stratified analyses. Matching will be based on propensity score weighting. We will compare the primary patient-level outcome (total quality of life score) between our

NAVIGATE and the U.S. RAISE study NAVIGATE groups over two years (baseline, 6 months, 12 months, 18 and 24 months). At each time point, we will use percentage change in total QLS score, along with 95% confidence interval from the RAISE study and the present study. Using the MAIC approach, mean results with overlapping 95% confidence intervals are taken to indicate that the interventions produced equivalent results.

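### The plan sets no single start date for the non-EPI control's outcome year, and its matching rule lets that year begin before the control's own first diagnosis

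*Combined protocol and SAP*

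**What the plan says.** All of this stands in section 4, under System Level Outcomes + Analytic Plan (Objective 2).

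The Data Sources paragraph defines the second control population as "FEP patients with no EPI contact". The Matched Controls paragraph then gives three time rules that apply to these patients:

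- They are matched "at time of first diagnosis for those patients not attached to EPI programs". No tolerance is given.
- For all controls: "We will match non-NAVIGATE to NAVIGATE subjects based on year of index diagnosis and caliper of the propensity score". The caliper width is not given.
- For all controls: "Non-NAVIGATE Subjects will be assigned the same admission date as NAVIGATE subjects".

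Incident status rests on a look-back: "subjects will not have had a non-affective psychotic disorder diagnosis within five years of the matching date". The matching date is not defined.

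The System Outcomes paragraph sets the window: "Our primary outcome is number of psychiatric hospitalization days in the year following NAVIGATE admission". The Statistical Analysis paragraph repeats the one-year window and adds: "We will subsequently model total hospital days adjusting for covariates".

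The Covariates paragraph lists diagnosis type, "source of index diagnosis (hospitalization, outpatient visit"), substance-related history and prior mental health service use. It does not list time since diagnosis.

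**The concern.** Psychiatric hospital days are likely to depend on where a patient is in the illness, and the plan itself recognises that the index diagnosis may be made in hospital. The two groups therefore need to start the outcome year at a comparable point.

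Under the year-of-diagnosis rule with an assigned date, a control first diagnosed in November can be given a partner's March admission date. The control's year then opens eight months before the control is a case. If the diagnosis is made during an admission, that stay counts as outcome, whereas the partner's equivalent stay came before time zero. Two further effects follow for such a control. Diagnosis type and source enter the propensity score although they arise after the start date. Survival up to diagnosis is guaranteed by selection, and mortality is among the system outcomes in section 3.1.

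If the analyst instead starts the control's year at first diagnosis, the control is diagnosed at the start. That contradicts the assigned-date sentence, however, and control follow-up then begins earlier in the illness than the partner's by the whole diagnosis-to-admission lag. Analysts following the same paragraph could produce different primary comparisons.

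**Working it through.** The plan gives no figure for this comparison to reproduce. The check compares the rules and then illustrates what they allow.

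**The rules side by side**

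- First diagnosis and the assigned admission date coincide only if the control happened to be diagnosed on that date.
- Year of index diagnosis is looser than either. Two people in the same calendar year can differ by almost 12 months in either direction.
- The look-back does not close the gap. Counted from the control's first diagnosis, it is an ordinary incident-case check and says nothing about the assigned date. Counted from the assigned date, it removes controls with a non-affective psychosis diagnosis in the preceding five years and leaves mainly those diagnosed on or after the start.

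**Illustration (a): match on year, then assign the date**

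Assumptions, none from the documents: the NAVIGATE patient's diagnosis date Dn and the control's Dc are independent and uniform over the same 12 months; the lag L from diagnosis to admission is fixed; the caliper is ignored. The assigned date is Dn + L.

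- Mean absolute difference in time since diagnosis: E|Dn − Dc| = 12/3 = 4.0 months. Mean signed difference: 0.
- Share with start before the control's diagnosis: P(Dc > Dn + L) = (1 − L/12)²/2.
- Share already diagnosed but more recently than the partner: 0.5 minus that share.
- Share diagnosed longer ago than the partner: 0.5.
- Mean pre-diagnosis days over all controls: 365 × (1 − L/12)³/6.

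| Lag (months) | Start before diagnosis | Diagnosed, more recently than partner | Diagnosed longer ago than partner | Mean pre-diagnosis days |
|---|---|---|---|---|
| 0 | 50% | 0% | 50% | 61 |
| 3 | 28% | 22% | 50% | 26 |
| 6 | 12.5% | 37.5% | 50% | 8 |
| 12 | 0% | 50% | 50% | 0 |

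Example at 3 months: (1 − 0.25)²/2 = 0.281, and 365 × 0.75³/6 = 25.7 days. A simulation of 2 million pairs agreed with the pre-diagnosis shares and days.

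Averaging the same formula over a variable lag gives pre-diagnosis shares of 42%, 31% and 22% for exponential lags with means of 1, 3 and 6 months, and 17% for a lag uniform on 0 to 12 months.

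These are not upper bounds. A NAVIGATE patient whose diagnosis is recorded only after admission has a negative lag. At one month after admission the share is 1 − (11/12)²/2 = 58%.

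**Illustration (b): a tolerance w on diagnosis date, then assign the date**

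With Dc − Dn uniform on (−w, w), the mean absolute mismatch is w/2: 0.5 months at w = 1 and 1.5 months at w = 3. The pre-diagnosis share is (w − L)/(2w) for L below w and zero from L = w. A tolerance alone therefore still leaves 50% at L = 0. Requiring diagnosis on or before the assigned date makes the share zero by construction.

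**Illustration (c): first diagnosis as the control's index**

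The mismatch equals the lag: 0, 3, 6 or 12 months in the cases above.

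**The case against.** The best defence is that a matching variable and a start date do different jobs. Matching on first diagnosis and then assigning the partner's admission date is coherent and would roughly equalise time since diagnosis. Using type and source of diagnosis as baseline covariates also suggests that the authors pictured controls as already diagnosed. Much of this stands: with a stated tolerance the design would be sound. But no tolerance is given, the explicit matching sentence says only year, and the expectation that controls are diagnosed at baseline is an inference from the covariates, not a rule. Prior service use and source of diagnosis are only partial proxies for time since diagnosis.

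Three stronger readings should be resisted.

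- A reader might infer that the comparison is tilted towards NAVIGATE because controls' diagnosing admissions are counted. The documents do not support a direction. Pre-diagnosis time may also carry few hospital days, and under illustration (a) half of the controls are further from diagnosis than their partner.
- A reader might infer that no reading of the plan has the control diagnosed at the start. Taking first diagnosis as the index does, at the price of contradicting the assigned-date sentence.
- A reader might infer that only non-EPI controls are affected. The assigned-date sentence covers EPI controls too, and their match on program admission date in the provincial assessment database (OCAN) has no stated tolerance. The problem is greatest for non-EPI controls because they have no admission event of their own.

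**Conclusion.** The point holds as a defect in the definition of time zero for one of the two comparisons on the primary system outcome. Followed literally, matching on year of diagnosis and assigning the partner's date allows outcome time before the control's diagnosis. It also lets time since diagnosis differ within a pair by up to a year, with no listed covariate to correct for it. The alternative reading avoids pre-diagnosis time but starts control follow-up earlier in the illness by an unstated lag.

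The 4.0-month mean mismatch and the 50%, 28%, 12.5% and 0% shares rest on assumed uniform, independent dates and assumed lags. They show what the wording permits, not what the data will show. Neither the direction of bias nor its size in hospital days can be derived from the documents. It should be settled before matching is run.

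**What to change.** For the non-EPI comparison:

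1. Keep the assigned admission date as the single time zero for both members of a pair. Say whether NAVIGATE admission means EPI program admission or study entry, because Clinical Assessments in section 3.3 allows entry up to a year into the program.
2. Replace year of index diagnosis with a stated tolerance on first-diagnosis date. One to three months is an assumed range for illustration.
3. Require each control to be alive and first diagnosed on or before the assigned date.
4. Add time since first diagnosis to the propensity model, measured at the assigned date. Candidate dates must then be set before the score is fitted.
5. Count the five-year washout back from the control's first diagnosis.
6. Give a rule for NAVIGATE patients with no recorded diagnosis before admission.

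For EPI controls, state a tolerance on OCAN admission date.

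Steps 2 and 3 leave a small residual imbalance at short lags. At L = 0 eligible controls lie in (−w, 0), so on the uniform assumption they are w/2 further from diagnosis: 0.5 or 1.5 months at w = 1 or 3. Step 4 addresses this.

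An alternative, or a sensitivity analysis, is to start the control's year at the partner's diagnosis-to-admission interval after the control's own diagnosis. That equalises time since diagnosis but gives up calendar alignment. With year-only matching and the same assumptions, the mean calendar offset is 4.0 months, which should be disclosed.

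The cost is extra matching code on ICES sources the plan already lists, with no new data collection. Some NAVIGATE patients may go unmatched; the number should be reported.
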